#### 8.7.4. Vital Signs

The following Vital Signs measurements will be reported for this study:

- Systolic Blood Pressure (mmHg)
- Diastolic Blood Pressure (mmHg)
- Heart Rate (bpm)
- Respiratory rate (breaths/min)
- Body temperature (°C)
- Weight (kg)
- BMI (kg/m^2)
  - Observed values and changes from baseline will be presented by visit and treatment group.

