The primary endpoint will be the mean change from BC of the average daily OPP score during TRC3. The OPP will be calculated for each cycle as the total of OPP scores reported during the cycle divided by the number of days during the cycle in which the score was reported. For participants who discontinue early, their last cycle will be associated with the cycle number at entry into the cycle. The primary analysis will be conducted using all participants with a post-treatment OPP measurement and will use a longitudinal model. The response vector for the model will be change from BC in the average OPP during TRC1, TRC2, and TRC3. Model terms will include the respective baseline, treatment, time (ie, cycle), and treatment-time interaction, allowing for the inclusion of individual outcomes over time (cycle). An unstructured error structure will be assumed. If nonconvergence is encountered, compound symmetry (CS) and first-order autoregressive AR(1) error structures will be considered.

Least squares mean change from baseline for each treatment group, with corresponding standard errors will be provided. Estimated treatment differences (each active treatment group versus Placebo) with corresponding 95% confidence intervals and 2-sided p-values will also be provided for each active treatment group. No missing data will be imputed for the primary analysis.

Supportive analyses will be conducted using an analysis of covariance (ANCOVA) on the change from baseline to the TRC3, with treatment as a fixed factor and baseline OPP as a covariate.

Secondary endpoints assessing change in continuous endpoints over time (either measurements within the cycle or at an individual visit) will use longitudinal models as described for the primary endpoint and/or ANCOVA models. Changes from SC to SFC will be compared using ANCOVA models using all participants with an OPP measurement during SFC. Select longitudinal models which focus on TRC1 and TRC2 may exclude TRC3 from the model. An unstructured error structure will be assumed for all longitudinal models. If nonconvergence is encountered, CS and AR (1) error structures will be considered.

Primary Safety Analysis:

The proportions of participants who experienced the following will be summarized

- A treatment-emergent adverse event (TEAE)
- Premature discontinuation of study treatment due to an AE

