- Changes from baseline to EOS abnormalities in clinical laboratory assessments, vital signs, and physical and gynecological examination

Pharmacokinetics:

- PK analysis set: The PK analysis set is a subset of the Safety analysis set (SAF) and will include all participants who received at least 1 dose of OG-6219 and have at least 1 quantifiable OG-6219 concentration.
- PK analysis set for noncompartmental analysis: The PK analysis set for noncompartmental analysis (NCA) will include all participants in the PK analysis set who chose intensive PK sampling in Day 1 (CC) and CC. Intensive PK sampling is optional where a separate consent would be provided.

OG-6219 and its primary metabolite FOR-1011 concentrations (all participants receiving OG-6219) will be summarized by treatment, study visit, and scheduled time for the PK analysis set, as appropriate.

Pharmacodynamics:

- PD analysis set: The pharmacodynamic (PD) analysis set is a subset of the SAF and will include all participants who received at least one dose of OG-6219 or Placebo and have at least 1 post-dose evaluable PD endpoint without protocol deviations or events affecting the PD results.

The PD and exploratory endpoints and change from baseline results will be summarized by treatment and scheduled time, where appropriate, for the PD analysis set.

Interim analysis (IA):

There will be no IA CCI. An interim psychometric analysis using blinded data will be performed to affirm methods for establishing pain responder cutoffs.

Data Monitoring/Other Committee: Yes

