3.0 OBJECTIVES AND ENDPOINTS

This is a double-blind, Placebo-controlled, parallel group, randomized study aimed to assess the efficacy, safety, and tolerability of OG-6219 in adult participants with moderate to severe ERP (OPP, DYS, and NMPP). The study objectives and endpoints are outlined in Table 1.

Table 1 Study Objectives and Endpoints

Objectives	Endpoints
Primary Endpoints The following primary efficacy endpoint will be assessed comparing Group A (CCI BID), B (CCI BID), C (CCI BID) with Group D (Placebo)	

 To evaluate the efficacy of 3 dose levels of OG-6219 (Group A, B, C) versus Placebo (Group D) in reducing OPP during TRC3, as measured by a NRS in the eDiary 	
 Change from BC to TRC3 in the mean OPP score^a
The following primary safety endpoints will be assessed for Group A (CCI BID), B (CCI BID), C (CCI BID) and Group D (Placebo)	

 To evaluate the safety and tolerability of OG-6219 	
 Proportion of participants who experienced any AEs/SAEs Abnormalities in clinical laboratory assessments, vital signs, and physical examination Proportion of participants who prematurely discontinued study treatment due to AEs/SAEs
Secondary Efficacy Endpoints The following secondary endpoints will be assessed comparing Group A (CCI BID), B (CCI BID), C (CCI BID) with Group D (Placebo)	
1. To evaluate the efficacy of 3 dose levels of OG-6219 (Groups A, B, C) versus Placebo (Group D) in reducing DYS during TRC3, as measured by a NRS in the eDiary	
 Change from BC to TRC3 the mean DYS score
2. To evaluate the efficacy of 3 dose levels of OG-6219 (Groups A, B, C) versus Placebo (Group D) in reducing NMPP during TRC3, as measured by a NRS in the eDiary	
 Change from BC to TRC3 the mean NMPP score
3. To evaluate the efficacy of 3 dose levels of OG-6219 (Group A, B, C) versus Placebo (Group D) reducing dyspareunia during TRC3, as measured by a NRS in the eDiary	
 Change from BC to TRC3 in the mean dyspareunia score

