9.4.7.2 Vital Sign Assessments

Results of vital sign parameters (including weight and BMI) and changes from baseline will be summarized descriptively. Results will also be listed by participant.

CCI

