# **8. STATISTICAL METHODS**

## **8.1. General Methodology**

### **8.1.1. Summary tables, listings, and figures**

All data will be listed and summarized with descriptive statistics in summary tables.

Continuous variables will be summarized for both the measured values and the change from baseline value, using the number of observations, mean, standard deviation (SD), median, minimum, and maximum. Categorical and ordinal variables will be summarized with counts and percentage for each category.

Box-and-whisker plots will be used to visualize efficacy endpoints by timepoint and treatment. Box-and-whisker plots will also be used to visualize laboratory data, vital signs, and ECG measurements. The results of the main efficacy analyses will be illustrated by plotting differences vs. placebo with 95% CIs for each OG-6219 dose group vs. cycle (or visit).

Mean values for each day relative randomization will be plotted by treatment group for OPP, number of rescue medication tablets used, and interference with daily activities.

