#### 8.7.6.5. PHYSICAL, GYNECOLOGICAL AND BREAST EXAMINATION

Physical, gynecological and breast examination findings after ICF are recorded in the eCRF AE page and will be presented in the AE listing. A listing of gynecological examination assessments in participants who had abnormal PAP smear results will be provided.

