## 10. CHANGES TO PROTOCOL-PLANNED ANALYSES

There were no changes to the analyses planned in the study protocol.

The study protocol did not include a description of the estimand. This has now been included in the SAP.

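### Vital-sign and examination abnormalities are part of a primary safety endpoint, but the SAP defines no abnormal vital sign, counts no women with one, and gives examinations no by-arm result of their own

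*SAP*

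**What the plan says.** **Endpoint.** Protocol 3.0 (Table 1) has three primary safety endpoints. The middle one is "Abnormalities in clinical laboratory assessments, vital signs, and physical examination", and SAP Table 1 repeats it. The other two are stated as proportions of participants; this one is not.

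**Measure.** The primary safety analysis in the Protocol 1.1 synopsis opens with "The proportions of participants who experienced the following will be summarized". Its third item is "Changes from baseline to EOS abnormalities in clinical laboratory assessments, vital signs, and physical and gynecological examination".

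**Protocol body.** Section 9.4.7.2 is purely descriptive: "Results of vital sign parameters (including weight and BMI) and changes from baseline will be summarized descriptively".

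**SAP, vital signs.** Section 8.7.4 says "Observed values and changes from baseline will be presented by visit and treatment group". Section 8.1.1 supplies the statistics for measured values and changes, "using the number of observations, mean, standard deviation (SD), median, minimum, and maximum", and adds box-and-whisker plots for vital signs.

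**SAP, examinations.** Section 8.7.6.5 says of physical, gynecological and breast examinations that "examination findings after ICF are recorded in the eCRF AE page and will be presented in the AE listing".

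**SAP, changes from protocol.** Section 10 says "There were no changes to the analyses planned in the study protocol", apart from adding the estimand.

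**The concern.** An endpoint defined as abnormalities needs two things before it can be reported: a rule for what is abnormal, and a count of participants who meet it. The SAP supplies both for laboratory tests and ECG but neither for vital signs. Examination findings have a listing but no summary that isolates them.

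Protocol 2.3.1 relies on vital signs, with serum chemistry and ECG, to monitor cardiovascular function. The question that abnormality data answer is how many women in each arm had a marked change. A by-visit summary of a continuous variable does not answer it. If limits are chosen only after unblinding, the count becomes an unplanned analysis, which SAP Section 2 requires to be identified as such.

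**Working it through.** The plan gives no figure for this endpoint, so the check is a trace from endpoint to output, followed by an illustration.

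**Trace**

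| Primary safety item | SAP output | Abnormality rule? | Participant count by arm? |
|---|---|---|---|
| Any AE/SAE | 8.7.1, TEAE tables | not needed | yes |
| Discontinuation due to AE | 8.7.1.2 | not needed | yes |
| Laboratory abnormalities | 8.7.2 shift tables, 8.7.2.1 low/normal/high, 8.7.2.2 liver criteria | yes | yes |
| Vital-sign abnormalities | 8.7.4 with 8.1.1 | none | none |
| Examination abnormalities | 8.7.6.5 AE listing; indirectly 8.7.1.1 | investigator judgement (Protocol 8.3.1) | not as a separate item |

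ECG, a secondary safety endpoint, has shift tables and QTcF threshold counts in SAP 8.7.3.

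**What the AE route covers.** Protocol 8.3.1 sends clinically significant examination changes to the AE page. Protocol Appendix 4 does the same for vital signs that the investigator judges clinically significant. Protocol 9.4.7.1 makes the TEAE tables by treatment. Three limits remain:

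- The tables are by system organ class and preferred term, so an examination finding is not recognisable as one.
- The TEAE window in SAP 8.7.1 closes 14 days after last dose. Protocol 8.4.1 puts EOS 30 days after last intake. The last 30 − 14 = 16 days fall outside the SAP's tables and reach only the listing.
- Entry depends on individual judgement, not a common limit.

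**What the descriptive route covers.** SAP 8.1.4 restricts by-visit summaries to scheduled time points; unscheduled readings are assured only in listings. The maximum is one woman's value per visit and arm, so it is the same whether one woman or five had a large rise.

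**Illustration.** n = 95 per arm (SAP 4.3: 380/4). The documents give no vital-sign event rate or SD, so the rest is assumed: k women in one arm have a 30 mmHg systolic rise, and the SD of change is 8 to 16 mmHg.

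- Shift in arm mean = (k/95) × 30. For k = 2, 5, 10: 0.63, 1.58, 3.16 mmHg.
- 95% half-width of a difference in means = 1.96 × SD × √(2/95). For SD = 8, 12, 16: 2.3, 3.4, 4.6 mmHg.
- For k = 5 the shift lies inside the half-width for any SD above 1.58 / (1.96 × 0.1451) = 5.6 mmHg. For k = 10 it exceeds the half-width at SD 8 but not at SD 12.
- As a count, k = 5 is 5/95 = 5.3% against, say, 0/95. The two-sided Fisher p-value is about 0.059. If both arms had a 5% rate, the 95% half-width of the difference would be 1.96 × √(2 × 0.05 × 0.95/95) = 6.2 percentage points. The count is thus descriptive too, but it states the quantity the endpoint names.

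**The case against.** The strongest reply is that the SAP follows the body of the protocol. Section 9.4.7.2 asks only for descriptive vital-sign summaries, and SAP 8.7.4 delivers them. The proportion wording stands only in the synopsis, in an item that is hard to parse, and Table 1 does not attach a proportion to this endpoint. This stands: the mismatch lies first within the protocol. A reader might infer that SAP Section 10 is simply wrong to declare no changes; the documents do not go that far. But the endpoint in both Table 1s is still abnormalities, and SAP 8.7.4 does not say what an abnormality is.

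A reader might infer that the SAP reports only mean vital signs. It does not: SD, median, minimum, maximum and box plots are planned, and all data are listed. A 30 mmHg rise at a scheduled visit would move the maximum, and the listings would show every affected woman. What is missing is the classification and the count.

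A reader might also infer that examination findings have no by-arm result at all. That is too strong. Clinically significant changes must be recorded as AEs and are counted in the TEAE tables if treatment-emergent.

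Finally, outside the AE page the documents show no post-consent record of whether an examination was normal, so a full abnormality table may not be derivable.

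**Conclusion.** The gap is real and limited. For vital signs, the SAP as written does not produce the endpoint that both documents name: it has no abnormality rule, no shift table and no count of women. For examinations, there is no dedicated by-arm result, only the listing and partial, unlabelled coverage in the TEAE tables up to 14 days after last dose.

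This concerns two components of one of the three primary safety endpoints. It would be wrong to conclude that the primary safety analysis as a whole is missing: AE incidence, discontinuation due to AEs and laboratory abnormalities all have outputs.

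The illustration shows why a mean is a poor substitute for a count. It rests on an assumed 30 mmHg rise, assumed numbers of women and an assumed SD of 8 to 16 mmHg. It does not show that a signal would be invisible, because the maximum and the listings remain. The conclusion about the gap depends on none of these figures.

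**What to change.** **Vital signs (SAP 8.7.4).** Set absolute and change-from-baseline limits before unblinding. Add one table giving, by arm, the number and percentage of women with at least one abnormal post-baseline value. Use every value collected through EOS, including unscheduled ones. The vital-signs row of the Protocol 1.3 schedule, as it reads in the available text, has no mark in the discontinuation column, so the table should not presume a reading there.

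**Examinations (SAP 8.7.6.5 and Section 10).** State that abnormalities are reported through AEs. If the AE page allows examination-related events to be identified, add a by-arm count of women with such an event through EOS, not only to 14 days after last dose.

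**Reconciliation.** Align the synopsis with Protocol 9.4.7.2, and record in SAP Section 10 which one governs.

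**Cost.** One or two extra safety tables and agreement on limits before unblinding. The vital-sign table needs no new data; the examination count depends on what the AE page holds.

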#### 8.7.5. COVID-19 Impact

To assess the impact that COVID-19 had on the trial, a listing of comments related to COVID-19 will be presented. This listing will also include information about visits and by-visit assessments that were impacted by COVID-19.

Additionally, a listing of participants who discontinued the study due to COVID-19, including participants who contracted the disease or discontinued for any other reason related to COVID-19, will be presented along with the specified text associated with discontinuation.

## 8.7.6. Other Safety Assessments

### 8.7.6.1. VAGINAL BLEEDING PATTERN

Participants records the presence of bleeding or spotting CCI in the eDiary. The CCI questions to assess bleeding pattern in the eDiary are “1a: During the past 24 hours, did you have any vaginal bleeding or spotting? If the response is “Yes”, then the next question is, “1b: During the past 24 hours, have you been on your period?”.

The following endpoints will be calculated:

- Mean change from BC to TRC1, TRC2, TRC3 in the number of days on period
- Mean change from BC to TRC1, TRC2, TRC3 in the number of days with irregular vaginal bleeding/spotting (i.e. days when question 1a was answered yes and question 1b was answered no)

The definition of cycles for the above endpoints will be different from the definition used for efficacy endpoints. For the vaginal bleeding endpoints, cycles will be defined based on start of menses dates only as below:

- Screening cycle (SC) – starts at the start of menses associated with CCI and ends the day before the start of menses associated with CCI
- Baseline cycle (BC) – starts at the start of menses associated with CCI and ends at the day before the start of menses associated with CCI
- Treatment cycle 1 (TRC1) – starts at start of menses associated with visit 4 and ends the day before the start of menses associated with phone contact C (PC1).
- Treatment cycle 2 (TRC2) – starts at the start of menses associated with phone contact C and ends the day before the start of menses associated with CCI
- Treatment cycle 3 (TRC3) – starts at the start of menses associated with CCI and ends the day before the start of menses associated with CCI
- Safety follow-up cycle (SFC) – starts at the start of menses associated with CCI and ends the day before the start of menses associated with CCI

The following summaries will be provided for vaginal bleeding pattern:

- Observed values and change from BC in the number of days on period by treatment cycle

and by treatment group

- Observed values and change from BC in the number of days with irregular vaginal bleeding/spotting by treatment cycle and by treatment group

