In this Phase 2a/b 4-arm PoC, dose-range study, treatment over CCI is intended to assess the effect of treatment with OG-6219 on efficacy, safety, and tolerability over 6 menstrual cycles.

While a previous study in cynomolgus monkeys exposed to OG-6219 for a total of CCI did not find any statistically significant changes in the mean CCI. An increase CCI in this Phase 2a/b study, if any, is expected to be fully and quickly reversible.

CCI

Also, no macroscopic or microscopic effect on bone tissue was observed in the CCI toxicology studies in rat and cynomolgus monkeys. However, no clinical experience on the effect of OG-6219 on systemic estrogen levels with longer exposure is available.

CCI

Effects on coagulation and lipid parameters as well as cardiovascular function will be monitored by serum chemistry, vital signs, and ECGs.

Participants will need to stop using any previous hormonal treatment for endometriosis as well as oral and other contraceptive treatment to enable assessment of the effect of HSD17 β 1 inhibition by OG-6219 on ERP, and menstrual regularity of the endometrium (refer to the [Table 2](#) and [Appendix 7](#)).

Embryo-fetal survival and development during the organogenesis phase of pregnancy was studied in pregnant rats and cynomolgus monkeys and no effect of OG-6219 treatment was found at the respective highest doses tested. However, as the effect of OG-6219 on fertility and early embryonic development and pre- and post-natal development has not been studied at this time, the risk of reproductive toxicity cannot be considered fully characterized. Therefore, necessary precautions to prevent pregnancy will be taken in this study. Participants will be informed about the risks to become pregnant and should not plan to become pregnant over the course of the study; only participants who are abstinent, or who are willing to reliably use an acceptable effective method for contraception as described in detail in the protocol (refer to the [Appendix 5](#)) and informed consent, or in whom safe contraception is achieved by a permanent method, will be eligible. A negative serum β -human chorionic gonadotropin (β -hCG) test prior to randomization and start of the treatment will be required, and monthly urinary pregnancy tests will be performed during the study implementation. Any pregnancy

will trigger withdrawal from study treatment, participant to expedited reporting and outcome of the pregnancy will be followed.

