[REDACTED] An increase in liver weight in both rats and cynomolgus monkeys likely attributable to CYP3A4 induction; however, no pre-clinical or Phase 1 data suggest any potential liver toxicity. In addition, no data on fertility and early embryonic development are available. CCI [REDACTED]
[REDACTED]
[REDACTED]

Therefore, in this current Phase 2a/b study, comprehensive panels assessing hematology, clinical chemistry, urinalysis parameters (CCI [REDACTED]), will be closely monitored. Refer to Section 8.4.6 for details of AESIs.

OG-6219 and its primary metabolite FOR-1011 are both metabolized mainly by CYP3A4 and were found to induce CYP3A4 in vitro. No clinical drug interaction studies were conducted to date. However, concomitant administration of OG-6219 with sensitive P-gp and BCRP substrates should be avoided (see Appendix 7).

To manage these risks, necessary precautions to prevent pregnancy will be taken in this study, including pregnancy tests prior to and during the study, and acceptable effective methods of contraception are required for participation. The effect of OG-6219 on systemic hormones, as well as general safety, including ECG and bone effects, will be closely monitored, including blood draws at different points during the first treatment cycle visit and each site visit at the start of next C treatment cycles, as well as during safety follow-up. Cycle length will be monitored by C self-reported bleeding pattern in an eDiary. The ECG measurements will be performed at relevant exposure time points, including T_{max} on Day 1 at the Randomization Visit and after achieving steady state (visit at CC [REDACTED] of the first menstrual cycle after randomization). CCI [REDACTED]
[REDACTED]

[REDACTED] Suicidality will be monitored throughout the study employing a validated questionnaire C-SSRS. Based on

determination of positive C-SSRS results for suicidality, the participants will be discontinued from the study medication and referred to a specialist at the Investigator's discretion for further evaluation. In addition, the positive results from C-SSRS evaluation will have to be treated as an SAE and reported to the Sponsor in a timely manner. Concomitant medications that are sensitive substrates, as well as moderate or strong inhibitors or inducers of CYP3A4 are prohibited. Concomitant medications that are sensitive substrates of P-gp or BCRP should be administered at least 4 hours apart from administration of OG-6219.

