4. To evaluate the daily use of Sponsor provided rescue medication taken for ERP at TRC1, TRC2, and TRC3	
 Change from BC to TRC1, TRC2, and TRC3 in the mean number of tablets of rescue medication for ERP Change from BC to TRC1, TRC2, and TRC3 in the proportion of days participant has used rescue medication for ERP

Objectives	Endpoints
5. To evaluate the change in the PGI-S Score at different time points	• Change in PGI-S Score from C to Phone Contact CCI
6. To evaluate the change in the PGI-C Score in different time points	• Percentage of participants with any improvement on the PGI-C at TRC1, TRC2, and TRC3
7. To evaluate the change in the EHP-30 domains (CCI) from BC to TRC3	• Change from BC to TRC3 in the EHP-30 Domain Scores
Secondary Safety Endpoints	
8. To assess the incidence of clinically significant ^d changes from V1 to C in bone biomarkers: ○ CCI ○	• Mean change from V1 to C in bone biomarker levels
9. To assess the incidence of any clinically significant ^d changes in laboratory parameters from V1 to CCI	• Proportion of participants with clinical parameters of significance from V1 to CC
10. To assess vaginal bleeding pattern over the 3 menstrual cycles (TRC1, TRC2, and TRC3) as captured in the eDiary	• Mean change from BC to TRC1, TRC2, TRC3 in the percentage of days with vaginal bleeding
11. To assess any potential change in the ECG parameters at CCI	• ECG parameter changes at CCI
Secondary PD / PK Endpoints	
12. To assess the change from CCI in serum hormone ^b concentrations	• Mean change from CCI in serum hormone levels
13. To assess any difference in serum hormone ^b concentrations at C between active treatment versus placebo	• Serum hormone levels comparing Group A (CCI BID), B (CCI BID), C (CC BID) with Group D (Placebo)
14. To assess any difference in serum hormone ^b concentrations at C between active treatment versus placebo	• Serum hormone levels at V7 comparing Group A (CCI BID), B (CCI BID), C (CCI BID) with Group D (Placebo)
15. To assess the PK of orally administered OG-6219 and the active metabolite FOR-1011 using sparse and intensive ^c PK sampling.	
 • Plasma concentrations of OG-6219 and FOR-1011 at scheduled assessments using sparse PK sampling during the treatment period. • C_{max}, T_{max}, and AUC_{tau} for both OG-6219 and FOR-1011 on C and C for the population with intensive PK sampling
CCI	

CCI

Note: Refer below and to [Figure 1](#)

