5. To evaluate the change in the PGI-S Score at different time points	
 
Change in PGI-S Score from C to Phone Contact CCI
 

6. To evaluate the change in the PGI-C Score in different time points	
 
Percentage of participants with any improvement on the PGI-C at TRC1, TRC2, and TRC3
 

7. To evaluate the change in the EHP-30 domains (CCI ) from BC to TRC3	
 
Change from BC to TRC3 in the EHP-30 Domain Scores
 

Secondary Safety Endpoints	
8. To assess the incidence of clinically significant b changes from V1 to C in bone biomarkers: 	
 
Mean change from V1 to C in bone biomarker levels
 

9. To assess the incidence of any clinically significant b changes in laboratory parameters from V1 to CC 	
 
Proportion of participants with clinical parameters of significance from V1 to CCI
 

10. To assess vaginal bleeding pattern over the 3 menstrual cycles (TRC1, TRC2, and TRC3) as captured in the eDiary	
 
Mean change from BC to TRC1, TRC2, TRC3 in the number of days on period and number of days with irregular vaginal bleeding/spotting
 

11. To assess any potential change in the ECG parameters at CCI	
 
ECG parameter changes at CCI
 

Secondary PD / PK Endpoints	
12. To assess the change from CCI in serum hormone c concentrations	
 
Mean change from CCI in serum hormone levels
 

13. To assess any difference in serum hormone c concentrations at C between active treatment versus placebo	
 
Serum hormone levels at V5 comparing Group A (CCI BID), B (CCI BID), C (CCI BID) with Group D (Placebo)
 

Version Date: 09JUN2025

- Treatment Cycle 1 is the period between the first day of menses associated with treatment start (C) to the day prior to the first day of next menses, regardless of number of days.
- Treatment Cycle 2 is the period between the first day of second menses after end of BC to the day prior to first day of next menses, regardless of number of days.
- Treatment Cycle 3 or EOT is the period between the first day of third menses after end of BC to either end CCI on study treatment, whichever occurs first.

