#### 8.2.4.3. GYNECOLOGICAL AND OBSTETRIC HISTORY

Gynecological history data will be summarized by treatment group for the following:

- Age of Menarche (years)
- Typical Cycle Length (days)
- Usual Duration of Flow (days)
- Usual Volume of Flow (Low/Moderate/Heavy)
- Presence of Clots during Flow (Yes/No)

Summaries of pregnancy history will include the number and percentage of study participants with previous pregnancies as well as descriptive statistics for the overall number of previous pregnancies (gravidity number), number of live births and the number of times the participant has given birth to a fetus with gestational age of 24 weeks or more (parity number).

- Number of Previous Pregnancies
- Gravidity
- Number of Live Births
- Parity

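### On-treatment cycle length, which the protocol says will be monitored, is not summarised by arm in the SAP, and the planned bleeding-day counts cannot stand in for it

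*SAP*

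**What the plan says.** - **Protocol 2.3.3 (Overall Benefit Risk Conclusion).** The paragraph on managing risks says that systemic hormones and general safety will be closely monitored, and adds: "Cycle length will be monitored by C self-reported bleeding pattern in an eDiary" (the isolated C marks a redaction).
- **Protocol 2.3.1 (Risk Assessment).** Previous hormonal treatment is stopped partly so that "menstrual regularity of the endometrium" can be assessed.
- **Protocol 5.1, inclusion criterion 4.** The entry range for cycle length is 21 to 32 days. Section 4.1 describes study cycles as of about the same length.
- **SAP 8.7.6.1.** The section sets its own cycle boundaries: "For the vaginal bleeding endpoints, cycles will be defined based on start of menses dates only as below". It then lists two summaries by cycle and arm. One is "Observed values and change from BC in the number of days on period by treatment cycle"; the other is the same for days with irregular bleeding or spotting.
- **SAP 8.2.4.3.** Typical cycle length is summarised as a gynecological history item. This is the only cycle-length variable that the SAP tabulates.
- **SAP 8.3.3.2.** Start-of-menses dates come from the eCRF and, where those are missing or repeated, from an eCOA search rule. In one defined case the start date is set to a visit date.

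**The concern.** Cycle length is a simple functional sign of whether the drug disturbs the menstrual cycle. The protocol's rationale is treatment that leaves the hypothalamic-pituitary-gonadal axis unmodified. The Phase 1 exposure it cites lasted at most 14 days, less than one cycle, and Section 2.3.1 says there is no clinical experience of the effect on systemic estrogen with longer exposure. Here women are followed over several cycles, the start dates are derived, and the protocol says cycle length will be monitored. Under the SAP as written, the study report need not say whether cycles lengthened, shortened or stopped in any dose arm.

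**Working it through.** **1. Can the planned counts show a change in cycle length?** Take five period days.

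| Cycle length | Days on period (SAP count) | Share of cycle |
|---|---|---|
| 28 days | 5 | 5/28 = 17.9% |
| 35 days | 5 | 5/35 = 14.3% |

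The count is the same in both rows. Irregular-bleeding days need not change either. A woman with no further menses opens no later cycle under 8.7.6.1, so she adds no value to later columns. She appears only as a smaller n, mixed with dropout.

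**2. Does another part of the SAP cover it?** The history item in 8.2.4.3 describes the time before the study. The general statement in 8.1.1 that all data will be listed and summarised does not define this derived variable, or say what to do when the next menses is not seen.

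**3. How many women per arm?** SAP 4.3 gives 95 per arm, 10% dropout, SD 2.2 and a 1-point difference for mean OPP, with a two-sided 0.05 test and 84% power. The documents state no figure for cycle length, so this one is reproduced to fix the evaluable n.

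- Evaluable n = 95 × 0.9 = 85.5.
- SE = 2.2 × √(2/85.5) = 0.336.
- 1/0.336 − 1.96 = 1.01, which gives power 0.844 (0.840 with the noncentral t).

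The stated 84% reproduces.

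**4. What precision would a cycle-length comparison have?** Half-width of the 95% CI = t(0.975) × SD × √(2/n). The SD is that of the variable compared. The documents give none, so a range is assumed.

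| Assumed SD (days) | Half-width, 85.5 per arm | Half-width, 60 per arm |
|---|---|---|
| 2 | 0.6 | 0.7 |
| 3 | 0.9 | 1.1 |
| 4 | 1.2 | 1.4 |
| 5 | 1.5 | 1.8 |
| 7 | 2.1 | 2.5 |

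The 60-per-arm column allows for women whose next menses is not observed.

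For the share of cycles outside 21 to 32 days, half-width = 1.96 × √(2p(1−p)/85.5). An assumed placebo rate of 5% gives 6.5 percentage points, and 20% gives 12.

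**5. Would the primary-endpoint model give a sound estimate?** Not on its own. A length exists only once the next menses is seen. A very long or absent cycle is missing because it is long, so the missing-at-random assumption behind the SAP 8.3.5 model fails in the direction that hides lengthening.

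**6. Are the derived dates clean?** Not entirely. After randomisation, the eCOA search in SAP 8.3.3.2 begins 15 days after the previous eCRF start. Before randomisation it covers only days 36 to 4 before a given visit. Lengths that rest on these dates, or on a visit date, partly reflect the rule.

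**The case against.** The protocol sentence promises monitoring, not a comparison between arms, and cycle length is not among the 15 numbered objectives. Monitoring of individuals is specified: under the Schedule of Activities, a delayed menses triggers a pregnancy test and contact with the clinic and the sponsor. The hormonal question also gets formal results. SAP 8.6 compares gonadotropins, estrogens, progesterone and androgens with placebo by ANCOVA, and 8.7.6.2 does so for endometrial thickness. Menstrual disorders reported as adverse events would appear in the TEAE tables. All of this stands, and it limits the point to one missing functional measure.

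Three stronger readings are tempting and are not supported.

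- **That effects on the ovarian axis go unexamined, or that the protocol relies on cycle length to detect them.** The placebo-compared hormones contradict the first. The single sentence in 2.3.3 does not bear the second.
- **That the trial is known to have good precision for this question.** That depends on an assumed SD. The entry range is no guide to it, because eligibility restricts only the month before Visit 1 and on-treatment cycles are not truncated. The share of irregular cycles would be estimated loosely.
- **That the primary endpoint cannot be read without it.** Cycle boundaries do depend on menses, but nothing in the documents shows how far a plausible shift would move mean OPP.

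A related discrepancy should not be counted as support. Protocol objective 10 has the endpoint "Mean change from BC to TRC1, TRC2, TRC3 in the percentage of days with vaginal bleeding", while SAP Table 1 has "Mean change from BC to TRC1, TRC2, TRC3 in the number of days on period and number of days with irregular vaginal bleeding/spotting", and SAP section 10 declares no change. That needs its own reconciliation. The omission described here exists either way.

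What the objection does not remove is the gap itself. Hormone levels at single visits, and counts of bleeding days, do not report how long cycles were or whether they stopped.

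**Conclusion.** The point holds in limited form. The protocol says cycle length will be monitored as part of safety, and the SAP gives no by-arm summary of it on treatment. The planned counts cannot show cycle lengthening or absent menses. The hormonal question is partly answered elsewhere; the cycle-length question is not. A comparison with placebo would be precise to about ±0.6 to ±1.5 days if the SD is 2 to 5 days and 85.5 women per arm are evaluable, and to about ±2.1 days at SD 7. It would describe only cycles with an observed next menses. The primary analysis is unaffected. This is a cheap improvement to safety reporting, not a flaw in the design.

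**What to change.** Add to SAP 8.7.6.1:

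1. A descriptive table by arm of cycle length in days for BC, TRC1 and TRC2, and for TRC3 only where the next menses was observed, with change from BC.
2. Counts by arm of cycles shorter than 21 or longer than 32 days, and of women with no further menses on treatment, kept apart from women who stopped treatment early.
3. A flag for cycles whose start date came from the eCOA rule or was set to a visit date (SAP 8.3.3.2), with the table repeated without them.
4. If a dose-minus-placebo difference with 95% CI is shown, a label that it is conditional on an observed next menses, with the no-further-menses count beside it. The 8.3.5 model under missing at random should not be the sole result.

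The cost is one short table on dates already derived, with no new data and no change to any other analysis. If the SAP can no longer be amended before unblinding, the table can still be reported as unplanned, which SAP section 2 allows if it is identified as such.
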